4.1.19 Tumor Assessments

A pretreatment computerized tomography (CT) scan with contrast (unless contraindicated) is required of the chest, abdomen, and pelvis and any other disease sites (eg, neck) within 30 days before the first dose of study drug.

On-treatment CT scans with contrast (unless contraindicated) of the chest, abdomen, and pelvis and any other disease sites (eg, neck) will be done for tumor assessments at Week 7, 13, 19 (\pm 7 days) then every 12 weeks (\pm 10 days) thereafter or more frequently at investigator discretion. At all other visits, tumor assessments will be done by physical exam and laboratory results.

RECIST 1.1 guidelines ([Eisenhauer 2009](#)) will be followed for selection of measurable and nonmeasurable lesions and also with regard to the number of lesions to be assessed (refer to [Appendix 7](#) for more details on RECIST 1.1). Response will also be assessed by irRECIST (refer to [Appendix 8](#) for more details).

De-identified copies of all radiology results may be requested by the sponsor.

4.1.20 Early Termination Visit

An early termination visit is required for safety assessments as outlined in the Schedule of Assessments ([Appendix 4](#)). The early termination visit is not required for subjects who discontinue from the study within 10 days of a scheduled study visit.

4.1.21 Study Drug Accountability

See [Section 7.6](#).

4.2 INVESTIGATOR'S ASSESSMENT OF RESPONSE TO TREATMENT

Responses will be categorized as CR, PR, SD, or PD. The definitions of response in target lesions are provided in [Table 4-1](#). The definitions of response in nontarget lesions are provided in [Table 4-2](#).

Table 4-1. Evaluation of Target Lesions (RECIST)

Response Category	Definition
CR	Disappearance of all target and nontarget lesions including normalization of an elevated tumor marker level. Any pathological lymph nodes (whether target or nontarget) must have reduction in short axis to <10 mm.
PR	A $\geq 30\%$ decrease in the sum of the diameters of target lesions taking as a reference the baseline sum of the diameters.
SD	Neither sufficient shrinkage to qualify for PR nor sufficient increase to qualify for PD taking as reference the smallest sum diameters while on study.
PD ^a	At least a 20% increase in the sum of diameters of target lesions, taking as reference the smallest sum on study (this includes the baseline sum if that is the smallest on study). In addition to the relative increase of 20%, the sum must also demonstrate an absolute increase of at least 5 mm. (Note: the appearance of one or more new lesions is also considered progression).

Abbreviations: CR=complete response, PD=progressive disease, PR=partial response, SD=stable disease

- a. Transient apparent worsening of disease early in therapy or during temporary interruption of study therapy (eg, for drug-related toxicity or intercurrent illness) may not indicate true cancer progression. Refer to [Section 3.11](#) for more detailed information.

Evaluation of nontarget lesions: while some nontarget lesions may actually be measurable, they need not be measured and instead should be assessed only qualitatively at the timepoints specified in the Schedule of Assessments.

Table 4-2. Evaluation of Nontarget Lesions (RECIST)

Response Category	Definition
CR	Disappearance of all non-target lesions and normalization of tumor marker level. All lymph nodes must be non-pathological in size (< 10mm short axis).
Non-CR/Non-PD	Persistence of one or more non-target lesion(s) and/or maintenance of tumor marker level above the normal limits.
PD ^a	Uequivocal progression ^b of existing non-target lesions. (Note: the appearance of one or more new lesions is also considered progression).

Abbreviations: CR = complete response; PD =progressive disease.

- a. Transient apparent worsening of disease early in therapy or during temporary interruption of study therapy (eg, for drug-related toxicity or intercurrent illness) may not indicate true cancer progression. Refer to [Section 3.11](#) for more detailed information.
- b. Refer to RECIST 1.1 criteria for detailed explanation of “unequivocal progression”.

4.2.1 Determination of Response at Each Timepoint (RECIST)

The tumor response at each timepoint will be determined. [Table 4-3](#) provides a summary of the overall response status calculation at each timepoint.

Table 4-3. Timepoint Response (RECIST)

Target Lesions	Nontarget Lesions	New Lesions	Overall Response
CR	CR	No	CR
CR	Non-CR/non-PD	No	PR
CR	Not evaluated	No	PR
PR	Non-PD or not all evaluated	No	PR
SD	Non-PD or not all evaluated	No	SD
Not all evaluated	Non-PD	No	NE
PD	Any	Yes or No	PD
Any	PD	Yes or No	PD
Any	Any	Yes	PD

Abbreviations: CR = complete response; PD = progressive disease; PR = partial response; SD = stable disease; NE = nonevaluable.

4.2.2 Confirmation of Tumor Status and Determination of Best Overall Response (RECIST)

The best overall response (BOR) recorded from the start of treatment until tumor progression will be determined. Adjudication of BOR is based on evaluation of each successive set of 2 scans as indicated in [Table 4-4](#).

Table 4-4. Best Overall Response Assessment and Requirements for Confirmation (RECIST)

Response Category at First Timepoint	Response Category at Subsequent Timepoint	Best Overall Response
CR	CR	CR
CR	PR	SD, PD, or PR ^a
CR	SD	SD provided minimum criteria for SD duration met otherwise PD
CR	PD	SD provided minimum criteria for SD duration met otherwise PD
CR	NE	SD provided minimum criteria for SD duration met otherwise NE
PR	CR	PR
PR	PR	PR
PR	SD	SD
PR	PD	SD provided minimum criteria for SD duration met otherwise PD
PR	NE	SD provided minimum criteria for SD duration met otherwise NE
NE	NE	NE

Abbreviations: BOR = best overall response; CR = complete response; PD = progressive disease; PR = partial response; SD = stable disease; NE = nonevaluable.

a. If a CR is truly met at first timepoint, then any disease seen at a subsequent timepoint, even disease meeting PR criteria relative to baseline, makes the disease PD at that point (since disease must have reappeared after CR). Best response would depend on whether minimum duration for SD was met. However, sometimes 'CR' may be claimed when subsequent scans suggest small lesions were likely still present and in fact the subject had PR, not CR at the first timepoint. Under these circumstances, the original CR should be changed to PR and the best response is PR.

4.2.3 Immune-related Response Criteria (irRECIST)

RECIST 1.1 will be adapted to account for the unique tumor response characteristics seen with treatment of pembrolizumab. Immunotherapeutic agents such as pembrolizumab may produce antitumor effects by potentiating endogenous cancer-specific immune responses. The response patterns seen with such an approach may extend beyond the typical time course of responses seen with cytotoxic agents and can manifest a clinical response after an initial increase in tumor burden or even the appearance of new lesions. Standard RECIST may not provide an accurate response assessment of immunotherapeutic agents such as pembrolizumab. Therefore, RECIST 1.1 will be used with the adaptations described for irRECIST ([Appendix 8](#)).

4.3 SAFETY FOLLOW-UP VISIT

Each subject should be followed for 30 (+ 7) days after his or her last dose of study drug (ie, the "safety follow-up visit") to monitor for resolution or progression of AEs (see

[Section 6.2.6](#)) and to document the occurrence of any new events, regardless of whether the subject receives a new anticancer therapy or demonstrates disease progression within this timeframe. Subjects who withdraw consent for study treatment should still be encouraged to complete the safety follow-up assessments, but these assessments cannot be mandated if subject consent for further study participation is withdrawn. The Schedule of Assessments ([Appendix 4](#)) describes the procedures required for safety follow-up.

4.4 SURVIVAL

After discontinuing study therapy, subjects will be contacted approximately every 12 weeks until death, withdrawal by subject, lost to follow-up, or study terminated by the sponsor, whichever comes first.

4.5 MISSED EVALUATIONS

Missed evaluations should be rescheduled and performed as close to the original scheduled date as possible. An exception is made when rescheduling becomes, in the investigator's opinion, medically unnecessary or unsafe because it is too close in time to the next scheduled evaluation. In that case, the missed evaluation should be abandoned.

5.0 STATISTICAL METHODS OF ANALYSIS

5.1 GENERAL CONSIDERATIONS

Descriptive statistics (including means, standard deviations, and medians for continuous variables and proportions and confidence intervals [CIs] for discrete variables) will be used to summarize data as appropriate.

For the interim safety analysis (DLT review), enrollment of 6 subjects in the combination arm for DLT review is consistent with sample sizes used in oncology studies for determination of MTD. The trial employs the standard National Cancer Institute definition of MTD (dose associated with DLT in $\leq 17\%$ of subjects). Provided the DLT review period is cleared in the combination arm and this arm is not stopped early for futility or toxicity ([Section 5.5](#)), then up to 31 subjects will be added per arm.

The sample size for this 2-arm trial was determined by a Z-test for normal approximation of binomial distribution, based on one-sided $\alpha = 0.10$, 80% power, with projected response rates of 40% in pembrolizumab/acalabrutinib arm and 18% in pembrolizumab

arm. [REDACTED] PASS version 11 was employed to conduct the sample size calculation.

5.2 DEFINITION OF ANALYSIS POPULATIONS

The following definitions will be used for the efficacy and safety analysis populations.

All-treated population: All enrolled subjects who receive ≥ 1 dose of any study drug (either acalabrutinib or pembrolizumab). The safety and primary efficacy analyses will be performed on the All-treated population.

Efficacy-evaluable population: All subjects in the All-treated population who have ≥ 1 evaluable response assessment after the first dose of study drug (either acalabrutinib or pembrolizumab). Sensitivity analyses for efficacy will be carried out on the Efficacy-evaluable population.

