3.0 STUDY DESIGN

This clinical trial is a Phase 2, multicenter, open-label, randomized study evaluating pembrolizumab monotherapy and the combination of acalabrutinib and pembrolizumab in subjects who have recurrent or metastatic NSCLC.

Subjects meeting the eligibility criteria for the study will be randomized 1:1 to one of the following arms:

Arm 1: Pembrolizumab 200 mg administered as an IV infusion every 3 weeks (Q3W)

Arm 2: Acalabrutinib 100 mg administered PO BID plus pembrolizumab 200 mg IV Q3W

Acalabrutinib treatment can continue for subjects who are tolerating therapy and not progressing. Pembrolizumab treatment is for 24 months from the date of first dose for subjects who are tolerating therapy and not progressing. Subjects who progress on the combination of pembrolizumab and acalabrutinib will discontinue study treatment while those with progression of disease in the pembrolizumab monotherapy arm will continue on pembrolizumab with the addition of acalabrutinib until a second disease progression or intolerance to therapy. For subjects who cross over to receive combination treatment, acalabrutinib treatment will begin at the next visit at which subjects are scheduled to receive pembrolizumab. The dose of acalabrutinib for these subjects will be determined based on the DLT review of Arm 2. Disease progression will be determined based on irRECIST guidelines ([Appendix 8](#) and detailed in [Section 3.11](#)).

[figure not shown]
Pembrolizumab treatment can end for subjects with confirmed CR if treatment has been administered for at least 24 weeks and 2 doses of pembrolizumab have been administered after confirmation of CR. Treatment on this protocol can continue for a minimum of 12 months after the last subject is randomized.

All subjects will have hematology, chemistry, and urinalysis safety panels performed at screening. Once dosing commences (Day 1), all subjects will be evaluated for safety, including serum chemistry, serum amylase and lipase, and hematology. PD and PK testing will be performed during the first few months of treatment. Radiologic tumor assessments will be completed at baseline and at ~6-week intervals during the trial. Subjects who discontinue study drug for any reason other than disease progression,

death, lost to follow-up, or withdrawal of consent will be followed for tumor assessment until disease progression or initiation of any other anticancer therapies, whichever comes first.

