3.3.4 Enrollment and Randomization Procedures

Enrollment of a subject into the study will be performed according to the following procedure:

The study center will notify the sponsor when a clinically eligible subject is identified and is ready to screen, to ensure enrollment availability on the study.

After the subject has signed and dated the Informed Consent Form (ICF), all screening procedures have been completed, and eligibility has been confirmed, the subject can be officially enrolled into the study.

To enroll a subject, the study center will fax/email a completed Enrollment Confirmation Form to the sponsor. The enrollment date will be the date that the sponsor confirms enrollment. The sponsor will aim to fax/email a completed Enrollment Confirmation Form to the study center within 24 hours.

The treatment assignment is based on the randomization list generated by the sponsor before study enrollment begins.

The Enrollment Confirmation Form will contain treatment-arm allocation.

Treatment must begin within the screening window ([Section 4.1](#)) and after the site has received the treatment-arm allocation from the sponsor.

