5.4.4 Analysis of Efficacy Parameters

Disease Control and Response Rate

The individual and composite endpoints of response and progression will be determined. Tumor control will be documented at each assessment by response category (see [Section 4.2](#)) as defined for each response parameter, date that response is first documented, and date of disease progression. DCR will be defined as the proportion of subjects who achieve a SD, PR or CR. ORR will be defined as the proportion of subjects who achieve a CR or PR (see [Section 4.2](#)).

DCR and ORR will be calculated and the corresponding 2-sided 95% CI will be derived.

In addition to evaluation of DCR and ORR by RECIST 1.1 criteria ([Eisenhauer 2009](#)), these endpoints will also be evaluated by irRECIST criteria ([Appendix 8](#)), though the ORR by RECIST will be considered the primary endpoint.

Duration of Response

The duration of response (DOR) is defined as the interval from the first documentation of response to the earlier of the first documentation of definitive disease progression or death from any cause. Kaplan-Meier methods will be used to estimate event-free curves and corresponding quartiles (including the median). Data from surviving, non-progressing subjects will be censored and detailed censoring rules will be specified in the statistical analysis plan (SAP).

Progression-free Survival

Progression-free survival (PFS) is defined as the interval from the date of first dose of study drug to the earlier of the first documentation of objective disease progression or death from any cause. Kaplan-Meier methods will be used to estimate the event-free curves and corresponding quartiles (including the median). Data from surviving, non-progressing subjects will be censored and detailed censoring rules will be specified in the SAP.

Overall Survival

OS is defined as the time from date of the first dose of study drug until date of death due to any cause. Subjects who are known to be alive or whose survival status is unknown will be censored at the date last known to be alive. The analysis methods for overall survival will be similar to those described for progression-free survival.

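### The site knows the arm before dosing, yet every stated efficacy analysis and all scheduled survival contact depend on dosing, so a randomised but undosed subject would be missing from OS

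*Protocol*

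**What the plan says.** **Design and disclosure of the arm.** Section 3.0: "This clinical trial is a Phase 2, multicenter, open-label, randomized study". Section 3.3.4: "The Enrollment Confirmation Form will contain treatment-arm allocation", and treatment must begin "after the site has received the treatment-arm allocation from the sponsor". The same section fixes a usable date: "The enrollment date will be the date that the sponsor confirms enrollment".

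**Analysis sets.** Section 5.2 defines two. All-treated requires at least one dose: "The safety and primary efficacy analyses will be performed on the All-treated population". Efficacy-evaluable is drawn from All-treated and also needs a post-dose response assessment: "Sensitivity analyses for efficacy will be carried out on the Efficacy-evaluable population".

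**Time origins.** In Section 5.4.4, PFS "is defined as the interval from the date of first dose of study drug", and "OS is defined as the time from date of the first dose of study drug until date of death".

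**Follow-up.** Section 3.12 commits long-term follow-up to subjects with at least one dose. Section 4.4 starts survival contact, about every 12 weeks, once study therapy is discontinued. Appendix 4 footnote d uses the same trigger.

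**The concern.** A randomised comparison is protected by keeping every subject in the group to which chance assigned them. Here the arm is disclosed first and dosing comes second, so anyone who goes undosed is lost after the allocation is known. Every efficacy analysis that the protocol states then leaves that subject out. The planned sensitivity analysis cannot reveal the effect, because its set is narrower still.

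This is more than an analysis left to the SAP. The protocol itself fixes the sets, the time origins and the follow-up trigger. A SAP could add an ORR table with a wider denominator, but it could not recover deaths that no schedule asked anyone to record. At stake is mainly OS: the reader could not tell whether selection through dosing had moved it.

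**Working it through.** **1. Follow a randomised, undosed subject through the text.**
- Section 3.3.4: has an arm and an enrolment date.
- Section 5.2: is in neither efficacy set.
- Section 5.4.4: has no start date for PFS or OS.
- Sections 3.12 and 4.4 and Appendix 4 footnote d: has no scheduled survival contact, since each rule is triggered by having received or stopped therapy.
- Section 3.13: has not left the study, because being undosed is not a listed exit reason.

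**2. Denominator for the illustration.** The synopsis gives up to 37 per arm. This reproduces from Section 5.1 (40% vs 18%, one-sided alpha 0.10, 80% power, unpooled variance): (1.2816 + 0.8416)² × (0.40×0.60 + 0.18×0.82) / 0.22² = 36.1, rounded up to 37. The sample size is not in dispute.

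**3. Number undosed.** The protocol does not give it. Assumption: k = 1, 2, 3 or 4 of 37 per arm (2.7, 5.4, 8.1 or 10.8%).

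**4. OS median.** Assume exponential times, with undosed subjects having r times the hazard of dosed subjects. Put the dosed hazard at 1 and f = k/37. The dosed-only median is ln 2 = 0.693. The all-randomised median t solves (1 − f)·exp(−t) + f·exp(−r·t) = 0.5. The relative difference is ln 2 / t − 1. For example, with k = 4 and r = 3, t = 0.614, so 0.693/0.614 − 1 = +13.0%.

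| r | k=1 | k=2 | k=3 | k=4 |
|---|---|---|---|---|
| 0.5 | −1.6% | −3.2% | −4.8% | −6.4% |
| 1 | 0 | 0 | 0 | 0 |
| 1.5 | +1.1% | +2.3% | +3.5% | +4.7% |
| 2 | +2.0% | +4.0% | +6.1% | +8.2% |
| 3 | +3.0% | +6.2% | +9.5% | +13.0% |

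A positive value means that All-treated reads longer. The table leaves out the interval from randomisation to first dose. That interval is at most 28 days, because treatment must begin within the screening window (Sections 3.3.4 and 4.1.5).

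**5. ORR, for scale.** If the undosed would not have responded, the All-treated rate is the true rate × 37/(37 − k). A true 18% reads 18.5, 19.0, 19.6 and 20.2%; a true 40% reads 41.1, 42.3, 43.5 and 44.8%. In whole subjects at k = 4, with exact 95% intervals: 7/37 = 18.9% (8.0 to 35.2) against 7/33 = 21.2% (9.0 to 38.9), and 15/37 = 40.5% (24.8 to 57.9) against 15/33 = 45.5% (28.1 to 63.6). The shifts are small beside the intervals.

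**The case against.** **All-treated is legitimate here.** The RECIST 1.1 text in Appendix 7 (its Section 4.9.1) accepts all treated patients as a basis for phase II response conclusions, and the secondary objectives in Section 2.2 speak of subjects treated with each regimen. This stands. A reader might infer that the primary ORR analysis is wrong; the documents do not support that. Nor does Appendix 7 contradict the PFS origin: its Section 4.6.3 dates the duration of stable disease from randomisation in randomised trials and states no origin for PFS.

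**Few subjects will go undosed, and OS is already mixed.** Eligibility is confirmed before enrolment, the sponsor aims to return the allocation within 24 hours, both arms receive pembrolizumab, and monotherapy subjects who progress are to receive acalabrutinib as well (Section 3.0). The incentive to leave on learning the arm is therefore weak, and planned crossover affects OS whatever set is used. Both points stand. They limit the size of the problem, but they do not justify leaving deaths uncollected.

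**PFS gains little.** Also correct. Survival contact yields deaths, not scans, so the median shifts in the table should not be claimed for PFS.

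**Inflated false-positive risk.** A reader might infer that dosing-based selection raises the type I error. Section 5.4.4 states no between-arm test, and on the sample-size test the All-treated error could rise, stay near nominal or fall depending on who goes undosed. The documents give no basis for choosing a direction.

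**Undosed subjects are not barred from follow-up.** True under Section 3.13. The gap is that no contact is scheduled. A subject who withdraws consent cannot be followed under any wording.

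**Conclusion.** The point holds as a conditional weakness that is cheap to remove. If any subject is randomised but undosed, no stated analysis preserves the randomised groups, and survival data for that subject are not scheduled. If nobody goes undosed, ORR is unchanged and PFS and OS shift only by the interval to first dose.

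The plausible effect on the OS median is about −6% to +13%. This rests on an assumed 1 to 4 of 37 undosed per arm, exponential times and a hazard 0.5 to 3 times that of dosed subjects; at equal hazard it is zero. The direction cannot be known without follow-up. The point does not show an error in the primary endpoint, a PFS bias of that size or a changed type I error, and OS remains affected by planned crossover.

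**What to change.** - **Section 5.2:** keep All-treated as the primary ORR and safety set. Add an all-randomised set, with subjects analysed in the assigned arm. Use it for OS and PFS. Report ORR on it as a supplementary display, with undosed subjects counted as non-responders, and give the number undosed and the reasons by arm.
- **Section 5.4.4:** time OS and PFS from randomisation, using the enrolment confirmation date. Leave PFS censoring of undosed subjects to the SAP, where this section already places censoring rules.
- **Sections 3.12 and 4.4 and Appendix 4 footnote d:** extend the roughly 12-weekly survival contact to consenting undosed subjects.

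**Cost:** wording in these places and a few extra contacts. The sample size and the primary ORR set do not change. The supplementary ORR will read slightly lower if anyone is undosed, and is not itself neutral if only one arm loses subjects, so it should sit beside the All-treated figure and not replace it. The time origin moves up to 28 days earlier while scans stay scheduled from first dose.
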